Cover Page

Official Title of the study

The Safety and Efficacy of Mini-Pool IVIG as Loading and Maintenance Therapy for Children with Persistent Immune Thrombocytopenia: A Novel Approach for Low-Middle Income Countries

NCT Number:

Not yet assigned

Document Date:

July 2025

The Safety and Efficacy of Mini-Pool IVIG as Loading and Maintenance Therapy for Children with **Persistent** Immune Thrombocytopenia, A Novel Approach for Low-Middle income countries

Introduction:

Immune thrombocytopenia (ITP) occurs with an incidence rate of 1.6 to 3.9 per 100,000 patient-years, which increases with age and has a slight female preponderance [1]. It is an autoimmune disease characterized by an isolated decrease in the platelet count and an increased risk of bleeding. The pathogenesis is complex, affecting multiple components of the immune system and causing both peripheral destruction of platelets and impaired megakaryopoiesis in bone marrow. The diagnosis is typically made by excluding known thrombocytopenia causes. ITP can affect both children and adults. The American Society of Hematology (ASH) defines ITP as a generalized purpuric rash accompanied by a platelet count less than 100,000/ μ L and normal white blood cell (WBC) count and hemoglobin level. Primary ITP may be further categorized based on the timing and persistence of symptoms. Newly diagnosed ITP refers to the condition from the time of diagnosis to 3 months afterward. Persistent ITP arises when symptoms continue 3 to 12 months following the initial diagnosis. Chronic ITP indicates ongoing symptoms beyond 12 months from the initial diagnosis until resolution or further management. Refractory ITP includes cases that do not resolve with splenectomy. Severe thrombocytopenia, when platelet counts are below 20,000/ μ L, warrants medical treatment [2].

Management strategies have evolved significantly, emphasizing individualized treatment approaches based on disease severity, bleeding risk, and patient-specific factors. The latest therapeutic options, ranging from observation and first-line treatments such as corticosteroids and intravenous immunoglobulin (IVIG) to second-line therapies, including thrombopoietin receptor agonists and immunosuppressive agents.

The balancing of treatment efficacy with the potential side effects and long-term outcomes is very crucial for optimum management. There is emerging role of personalized medicine in optimizing care for children with ITP, highlighting recent advances in targeted therapies and the potential for future research to refine diagnostic and treatment paradigms [3].

Eltrombopag (ELT) is effective and safe in adult persistent/chronic immune thrombocytopenia (p/cITP); a proportion could achieve a sustained response off treatment (SRoT). A multicentre retrospective observational study was performed in November 2022 for children with p/cITP who used ELT alone for >2 months between January 2017 and November 2021. Clinical data of pre-, during and post-ELT were collected. SRoT was defined as maintaining a platelet count of $\geq 30 \times 10^9 /L$ without rescue therapy for at least 6 months off ELT. There were 43.3% and 25.9% achieved complete response (CR) and response (R). [4].

While IVIG is considered as safe and effective first line therapy for management of acute pediatric/adult ITP [5], yet there is no report on the role of IVIG as second line therapy for persistent/chronic ITP. One of the reasons might be the high cost of IVIG therapy compared to other standard therapies. El Ekiaby et al published a method for preparation of IVIG from mini-pools of plasma in blood bank environment using disposable medical devices produced by Swiss Company VIPS. The devices combine single use disposable bags and validated virus inactivation and IgG purification chemicals [6]. Mini-pool immunoglobulins proved safety and efficacy for management of acute pediatric ITP in a prospective randomized clinical trial [7]. The use of this new technology significantly reduces the cost of production of local mini-pool IVIG preparations. The use of locally produced mini-pool IVIG might be a safe and cost effective second line therapy.

Aim of the study:

Assessment of safety and efficacy of mini-pool IVIG as a second line therapy for management of pediatric persistent ITP.

Primary end points:

- 1-Bleeding score, duration, site and frequency calculated as BAT score
- 2-Frequency of hospital admission due to ITP critical bleeding episodes excluding hospital admission for Mini-Pool IVIG administration
- 3-Levels of platelet count during study period and its maintenance during subsequent 6 months after end of study period for patients with PC $> 30,000 / \mu L$

Secondary end points:

- 1-Record of adverse events
- 2-Patient/family satisfaction
- 3-School attendance and physical activity
- 4- Presence of a sustained response

Study protocol:

Three tertiary care Pediatric Hematology/Oncology centers will be enrolling children with persistent ITP “loss of initial response to first line therapy (steroids/IVIG) within 3-6 months”

Participating centers are, Ain Shams, Zagazig and Assuit Pediatric Hematology/Oncology

Inclusion Criteria:

- Age 1 – 10 years
- Gender: Males and Females
- Persistent ITP according to ASH definition
- No history of treatment with thrombopoietin agonists

Exclusion criteria:

- History of severe drug adverse events to IVIG
- Previous history of ICH
- Difficult venous access
- Congenital thrombocytopenia, secondary ITP and non-immune thrombocytopenia

Sample size

20 child with persistent ITP

6-Study period 3 – 6 months followed by 6 months observation for cases that showed remission off-therapy (SRoT >100,000, RoT >30,000 with no bleeding manifestations necessitating platelet enhancing therapy) after the end of the mini-pool IVIG therapy,

7-Study protocol highlights:

Infusion of 1 gm/kg of mini-pool IVIG as a loading dose over 6-8 hours, then repeat every 2-4 weeks as a maintenance dose of 0.5 gm/KG every 2 – 4 weeks according to platelet count at end of 2nd week for 5 subsequent doses

- Age at diagnosis, sex, family history of bleeding
- History of infection or vaccination before thrombocytopenia, onset of bleed acute or insidious onset
- Initial blood count at onset of the diagnosis, at enrollment and before IVIG infusion and 72 hours after end of IVIG infusion
- Repeat CBC:

- Platelet Count Below 50,000/ μ l repeat CBC weekly
- Platelet Count Above 50,000/ μ l repeat CBC every 2 weeks

-

-Record the following:

-Platelet count 72 hours after infusion, after 2 weeks and just before subsequent maintenance dose

- Infusion related adverse events
- Frequency and site of bleeding episodes according to BAT scoring
- Need for hospitalization
- School attendance
- Physical activities

-Early study termination:

- Severe adverse events
- Non-compliance (missing 2 consecutive visits)
- No improvement in platelet count after 3 infusions (< doubling basal pc or PC <30,000/mm³)

Quality of response

CR: platelet count $\geq 100 \times 10^9/L$ and absence of bleeding

R: platelet count $\geq 30 \times 10^9/L$ and at least 2-fold increase the baseline count and absence of bleeding

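### The enrolment sentence and the inclusion list describe persistent ITP in ways that do not select the same children, and the 3-6 month window has no start point

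*Protocol*

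**What the plan says.** The opening paragraph of the Study protocol section states "Three tertiary care Pediatric Hematology/Oncology centers will be enrolling children with persistent ITP" and at once explains the term as "loss of initial response to first line therapy (steroids/IVIG) within 3-6 months". On its face this requires three things: first-line treatment with steroids or IVIG, an initial response, and loss of that response in a stated window. It does not say whether the window runs from diagnosis, from the start of therapy or from the onset of response.

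The Inclusion Criteria identify the disease state by a different route: "Persistent ITP according to ASH definition". The only inclusion item on earlier treatment is "No history of treatment with thrombopoietin agonists". The exclusion list mentions IVIG only as a past cause of severe adverse events, which does not require exposure. Neither list asks for earlier steroids or IVIG, a response, or its loss.

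The document gives one definition of persistent ITP, in the Introduction: "Persistent ITP arises when symptoms continue 3 to 12 months following the initial diagnosis". It comes after a definition of ITP credited to ASH, but the sentence that opens the subcategories, "Primary ITP may be further categorized based on the timing and persistence of symptoms", does not name ASH as their source.

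The Aim of the study is "Assessment of safety and efficacy of mini-pool IVIG as a second line therapy for management of pediatric persistent ITP". The Sample size entry, "20 child with persistent ITP", repeats the term without saying which meaning applies.

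**The concern.** One term carries two meanings in the part of the Protocol that decides who enters. One meaning is a treatment history; the other is a time since diagnosis. A centre that screens against the inclusion list and a centre that screens against the enrolment sentence can reach different decisions on the same child.

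The study has 20 children at three centres and describes no control group. Each child is 1/20 = 5% of the sample, and no comparison arm would offset a difference in case mix. If centres apply different rules, it becomes unclear to which children the bleeding, admission and platelet results apply. Eligibility is fixed in the protocol, so this is not a matter that a statistical analysis plan would normally settle.

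**Working it through.** There is no stated figure to reproduce. The check sets the two texts side by side and applies them to example children. All other criteria are taken as met, and month 0 is diagnosis.

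**Inputs**
- Enrolment sentence (Study protocol, opening paragraph): first-line treatment, response, loss of response within 3-6 months; start point not given.
- Inclusion list: persistent ITP by the ASH definition. The Introduction's definition, symptoms 3 to 12 months after diagnosis, is used for its content. That link is an inference.
- Aim of the study: second-line therapy.

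**Cases**

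| Child | Inclusion list | Enrolment sentence |
|---|---|---|
| A: treated first-line, never responded, symptoms at month 4 | Met: 4 lies in 3-12 | Not met: no response to lose |
| B: never treated, symptoms at month 4 | Met: 4 lies in 3-12 | Not met: no first-line therapy |
| C: therapy from month 4, response lost at month 8, symptoms continuing | Met: 8 lies in 3-12 | Depends on the start point |
| D: therapy from month 0, response lost at month 4, enrolled with symptoms at month 9 | Met: 9 lies in 3-12 | Met: 4 - 0 = 4 from therapy and from diagnosis |

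**Child A** separates the two texts. The result does not depend on the 12-month limit, because month 4 is far from it.

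**Child B** separates them too, and also conflicts with the aim, since a treatment given to a never-treated child is not second-line.

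**Child C** shows the open start point:
- counted from the start of therapy, 8 - 4 = 4 months, inside 3-6;
- counted from diagnosis, 8 - 0 = 8 months, outside 3-6.

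This ambiguity lies within the enrolment sentence alone, so it remains however the two texts are combined.

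**Child D** marks the limit of the point. The enrolment window times the loss of response; the Introduction's window times the continuation of symptoms. One child can satisfy both while enrolling after month 6.

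**The case against.** The strongest reply is that the texts are meant to be read together. They stand a few lines apart and nothing presents them as alternatives. A child would need ASH-persistent ITP and, in addition, a lost first-line response; the second-line aim supports this. Children A and B would then be excluded at every centre. The reading is plausible, but the Protocol does not state it. The wording reads as an explanation of the term rather than as an added condition, and the condition is missing from the list against which centres would be expected to screen. Even if the reading is accepted, child C remains undecided.

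Other parts of the opposing case stand, and they limit what can be claimed:

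- A reader might infer that the upper limits of 6 and 12 months contradict each other. They do not in themselves, because the windows time different events, as child D shows.
- A reader might overlay the windows and report that they share 3 of 9 months. That assumes both run from diagnosis, compares different events, and says nothing about how many children are affected.
- A reader might treat 3 to 12 months as the ASH limit. The Introduction does not expressly say so.
- A reader might infer that the enrolled mix could not be described afterwards, because the listed history items omit prior first-line treatment and response. That list is headed as highlights and is not shown to be the full data collection.

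**Conclusion.** The point holds in this form: the enrolment sentence requires a first-line response and its loss, the inclusion list does not, and the 3-6 months have no start point. Screening by the list as written admits never-responders and never-treated children whom the enrolment sentence leaves out. The never-treated also fall outside the study's stated aim.

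The size and direction of any effect on results cannot be derived from the document. A mixed population arises only if centres read the rule differently, and it alters results only if outcomes differ by earlier treatment, earlier response or timing. The Protocol gives no figure for either. If outcomes do not differ, the effect is zero.

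The conclusion assumes that the Introduction's definition is the one the inclusion item refers to. If it is not, the document gives the criterion no content, which would also need correction. The open start point does not depend on this assumption. Which population is clinically right is not judged here. The correction should be made before enrolment because it decides who enters and costs little.

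**What to change.** Before enrolment, reconcile the enrolment sentence and the inclusion item into one criterion, placed in the Inclusion Criteria. It should state:

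- whether prior first-line treatment, an initial response, and loss of that response are each required, consistently with the second-line aim;
- for any time window, the event it times and the point from which it is counted;
- what is meant by the ASH definition, written out in the criterion.

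The opening paragraph and the Sample size entry should then refer to that criterion. Simply deleting the enrolment sentence would not be a repair: it is the only eligibility text that implies prior first-line therapy, so its removal would leave never-treated children eligible.

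Naming prior first-line treatment and response among the recorded history items is an optional addition that would help describe the enrolled children.

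The cost is one rewritten criterion and, if wanted, one history item. Once children have been enrolled under different readings, they cannot be re-selected.
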